3.2 Exclusion criteria

Subjects should not enter the study if any of the following exclusion criteria are fulfilled:

1. Type 1 diabetes or history of diabetic ketoacidosis
2. Pregnant or breast-feeding patients
3. $eGFR < 60 \text{ mL/min/1.73 m}^2$ (MDRD) on visit 1.
4. Indication of active liver disease (AST/ALT/total bilirubin $> 3 \times$ upper limits of normal) on visit 1.
5. Acute coronary syndrome, stroke or TIA within 3 months prior to randomization
6. Bariatric surgery within 2 years; treatment of anti-obesity drugs 3 months prior to randomization; any treatment leading to unstable body weight. (Unstable body weight is considered reliable in the judgment of the Investigator.)
7. Any kind of surgery using foreign metallic materials
8. History of bladder cancer or history of radiation therapy to the lower abdomen or pelvis at any time
9. History of any other malignancy within 5 years (with the exception of successfully treated non-melanoma skin cancers)
10. History of alcohol or drug abuse judged by physician within 3 months prior to randomization
11. Concomitant participation in any other clinical study.

Procedures for withdrawal of incorrectly enrolled subjects see Section 3.4.

3.3 Subject enrolment and randomization

120 subjects meeting all inclusion and none of the exclusion criteria will be randomized to the study. Estimated number of enrolled patients is approximately 160.

Subjects will be in open label treatment.

Subjects who discontinue the study will not be replaced.

The E-code is the only subject identification number to be used in CSRs and high level documents.

Investigator(s) should keep a record, the subject screening log, of subjects who entered pre-study screening.

The Investigator(s) will:

1. Obtain signed informed consent from the potential subject before any study specific procedures are performed.
2. Assign potential subject a unique enrolment number code.
3. Determine subject eligibility.
4. Randomize only eligible subjects

If a subject withdraws from participation in the study, then his/her enrolment code cannot be reused.

Randomization will be conducted strictly sequentially as subjects become eligible for randomization.

3.4 Procedures for handling incorrectly enrolled or randomized subjects

Subjects who fail to meet the eligibility criteria should not, under any circumstances, be enrolled or receive study medication. There can be no exceptions to this rule. Subjects who are enrolled, but subsequently found not to meet all the eligibility criteria must not be randomized or initiated on treatment, and must be withdrawn from the study.

Where a subject does not meet all the eligibility criteria but is randomized in error, or incorrectly started on treatment, the Investigator should inform the AstraZeneca study physician immediately, and a discussion should occur between the AstraZeneca study physician and the investigator regarding whether to continue or discontinue the patient from treatment. The AstraZeneca study physician must ensure all decisions are appropriately documented.

3.5 Methods for assigning treatment groups

Biostatistics group in CRO has the responsibility to generate the randomization scheme. The randomization scheme in blocks will be generated by computer software incorporating a random number generator. The randomization scheme can be balanced in blocks across the study.

3.6 Methods for ensuring blinding

Not applicable – This is an open-label study.

3.7 Methods for unblinding

Not applicable – This is an open label study.

3.8 Restrictions

Subjects should be instructed to abstain from all food and recommended not to use tobacco/nicotine products within 12 hours prior to each clinic visit and refrain from alcohol intake 24 hours prior to the visits (drinking water after midnight is allowed). Acceptable concomitant medications can be taken with water only.

Subjects should not take the investigational product and open-label metformin (and rescue medication if applicable) on the morning of the clinic visit.

If a subject comes to a visit without having followed the above instructions, then the subject will be re-scheduled for the entire visit (if possible within allowed time-window).

Subjects who are blood donors should not donate blood from enrolment until 12 weeks following their last dose of randomized treatment.

3.9 Discontinuation of investigational product

Subjects may be discontinued from investigational product (IP) in the following situations:

- Subject decision. The subject is at any time free to discontinue treatment, without prejudice to further treatment
- Adverse Event (including laboratory abnormality or intercurrent illness) which, in the opinion of the investigator, indicates that continued participation in the study is not in the best interest of the subject
- Major and/or frequent hypoglycaemic events, defined as ≥ 1 major event or recurring minor events (any recurrent events of hypoglycaemia, as judged by the investigator, not meeting the definition of major hypoglycaemic event)

- Calculated Creatinine-Clearance <60 ml/min or an increase in serum creatinine of ≥ 0.5 mg/dl above the baseline value confirmed at a repeated measurement within one week.
- Subject will become pregnant
- Use of (need for) any antihyperglycaemic medication other than investigational product and metformin. Insulin use for up to 14 days total during the study and up to 7 continuous days is permitted only in cases where:
 - Subjects are unable to take oral medications (for example during a gastrointestinal illness),
 - There is a documented illness or infection that requires additional therapy for maintaining glycaemic control.
- Severe non-compliance with the study protocol.

3.9.1 Procedures for discontinuation of a subject from investigational product

At any time, subjects are free to discontinue investigational product or withdraw from the study (i.e., investigational product and assessments), without prejudice to further treatment. A subject that decides to discontinue investigational product will always be asked about the reason(s) and the presence of any adverse events. If possible, they will be seen and assessed by an Investigator(s). Adverse events will be followed up (See Section 6) and all study drugs should be returned by the subject.

Randomized subjects who discontinue the study prematurely should immediately stop taking investigational product and complete the procedures described for Visit 7 (End of Treatment Visit), as soon as possible but not later than 7 days after discontinuation of investigational product. DXA and CT measurement should be performed as described for Visit 7.

If a subject is withdrawn from study, see Section 3.10.

3.10 Criteria for withdrawal

3.10.1 Screen failures

Screening failures are patients who do not fulfil the eligibility criteria for the study, and therefore must not be randomized. These patients should have the reason for study withdrawal recorded as 'Incorrect Enrolment' (i.e., patient does not meet the required inclusion/exclusion criteria). This reason for study withdrawal is only valid for screen failures (not randomized patients).

3.10.2 Withdrawal of the informed consent

Patients are free to withdraw from the study at any time (investigational product and assessments), without prejudice to further treatment.

Patients who withdraw consent for further participation in the study will not receive any further IP or further study observation. Note that the patient may be offered additional tests to withdraw safely.

A patient who withdraws consent will always be asked about the reason(s) and the presence of any adverse events (AE). The Investigator will follow up AEs outside of the clinical study. If a subject withdraws from participation in the study, then his/her enrolment/randomization code cannot be reused. Withdrawn subjects will not be replaced.

Patients will be considered lost to follow-up only if no contact has been established by the time the study is completed, such that there is insufficient information to determine the patient's status at that time. Patients who refuse continuing participation in the study, including telephone contact, should be documented as "withdrawal of consent" rather than "lost to follow-up." Investigators should document attempts to re-establish contact with missing patients throughout the study period. If contact with a missing patient is re-established, the patient should not be considered lost to follow-up and any evaluations should resume according to the protocol.

3.11 Discontinuation of the study

The study may be stopped if, in the judgment of AstraZeneca, study subjects are placed at undue risk because of clinically significant findings that:

- meet individual stopping criteria or are otherwise considered significant
- are assessed as causally related to study drug,
- are not considered to be consistent with continuation of the study

Regardless of the reason for termination, all data available for the subject at the time of discontinuation of follow-up must be recorded in the CRF. All reasons for discontinuation of treatment must be documented.

In terminating the study, the Sponsor will ensure that adequate consideration is given to the protection of the subjects' interests.

4. STUDY PLAN AND TIMING OF PROCEDURES

Study is planned to be conducted according to plan described in [Table 1](#).

This study is a 52-week, multi-centres, randomized, parallel-group, open, Phase IV study. All subjects will be enrolled by recruiting centres (centres treating patients with T2DM). Each enrolled subject will be referred to DXA measurement and abdominal CT scan.

The objectives of the study cover measurements at baseline, 4, 12, 24, 36 and 52 weeks. The primary efficacy end-point is to evaluate the effect of dapagliflozin 10 mg daily in

Clinical Study Protocol
Drug Substance Dapagliflozin
Study Code D1690L00067
Version 3
Date 07 June 2016

combination with metformin compared to glimepiride in combination with metformin on body composition in Korean T2DM subjects after 52 weeks of oral administration of open-label treatment.

Subjects with T2DM and inadequate glycaemic control ($\text{HbA1c} \geq 7.0\%$ and $< 10.0\%$) with stable metformin monotherapy ≥ 1000 mg/day for at least 8 weeks prior to enrolment will be eligible to enter the study.

The recruiting investigator will be the main point of contact for the subject and also responsible for the documentation of study data within the eCRF. All subjects do DXA measurement and abdominal scan scheduled to coincide with Visit 2 and Visit 7.

Local evaluation of the DXA will be conducted.

Table 1 Study Plan detailing the procedures

Study weeks	Screening (Baseline)	Randomisation	Treatment					End of Therapy	Rescue Visit ²
	0wk (-7...0 days)	0wk	4wks (+/- 7 days)	12wks (+/- 7 days)	24wks (+/- 7 days)	36wks (+/- 7 days)	52wks (+/- 7 days)	Planned if needed	
Visit	1	2	3	4	5	6	7	R	
Informed consent	0								
Demography	0								
Physical Exam ¹	0		0	0	0	0	0	0	
Medical/Surgical History	0								
Diabetes History	0								
12 lead ECG	0						0		
Height	0								
Weight	0		0	0	0	0	0	0	
BMI calculation	0		0	0	0	0	0	0	
Waist circumflex	0		0	0	0	0	0	0	
Pulse, blood pressure (SPB/DBP)	0		0	0	0	0	0	0	
FBG	0		0	0	0	0	0	0	
HbA1C	0		0	0	0	0	0	0	
CBC	0		0	0	0	0	0	0	
AST/ALT/total bilirubin	0			0	0	0	0	0	
BUN/creatinine	0			0	0	0	0	0	
Na/K/Cl	0			0	0	0	0	0	

4.1 Screening: VISIT 1

Procedures will be performed according to the Study Plan, see [Table 1](#).

Patients will obtain information regarding the study and sign informed consent for the study before any study related procedures are initiated.

Consented patients will be assessed to ensure that they meet eligibility criteria.

Demography, medical/surgical and diabetes history will be checked, 12 lead ECG will be conducted.

Physical exam will be conducted.

Height will be measured in cm (without shoes), weight in kg (light clothes and without shoes) and waist circumference (in cm). BMI calculation will be conducted. Pulse and blood pressure (SBP, DBP) will be measured.

Laboratory baseline test for efficacy and safety parameters will be conducted: FBG, HbA1c, CBC, AST, ALT, total bilirubin, BUN, creatinine, electrolytes, total cholesterol, triglyceride, HDL-cholesterol, urinalysis, hsCRP, adiponectin. All laboratory assessment will be done in central laboratory. Pregnancy test by dipstick should be performed for all WOCBP.

All serious adverse events occurring after signing the informed consent will be reported.

Concomitant diabetes and other medications will be checked.

Eligible patients will receive an enrolment code.

4.2 Randomization: VISIT 2

Eligibility criteria will be checked.

Subjects will be randomized to the treatment arm. Subjects who do not meet these criteria must not be randomized in the study.

DXA and abdominal CT baseline measurement will be conducted.

Diet and life-style counselling will be given to the subject.

Subjects will be given a diary to record hypoglycaemic events (symptoms).

All subjects will be instructed to constantly follow hygiene to avoid urinary tract infections.

Study drug will be dispensed according to randomisation. 1mg glimepiride will be dispensed first to the subjects who are allocated to glimepiride group. Metformin will be dispensed.

All serious adverse events will be reported.

Adverse Events will be collected from subject actually taking the IP.

4.3 Treatment Period: VISITS 3, 4, 5, 6

Physical exam contains measurement of weight, waist circumflex, pulse and blood pressure. BMI calculation will be conducted.

Subject diary will be reviewed for hypoglycaemic events. New diary will be dispensed to the subjects.

Subjects will be followed for laboratory assessment of efficacy and safety according to study plan:

- Visit 3: FBG, urinalysis
- Visit 4: FBG, HbA1c, AST, ALT, total bilirubin, BUN, creatinine, urinalysis
- Visit 5: FBG, HbA1c, CBC, AST, ALT, total bilirubin, BUN, creatinine, electrolytes, urinalysis
- Visit 6 : FBG, HbA1c, urinalysis

All laboratory assessment will be done in central laboratory.

Diet and life-style counselling will be given to the subject.

Concomitant medications will be checked.

Drug accountability of investigational product and metformin will be conducted.

Investigational product and metformin will be dispensed.

In case of glimepiride group, glimepiride can be up titrated to 2 mg to maintain glycaemic control at the discretion of the investigator after evaluation of glycaemic control in subjects. Glimepiride can be also down titrated to mitigate recurrent hypoglycaemic events at the discretion of the investigator but 0mg is not allowed. If further hypoglycaemic events occur with meeting the discontinuation criteria after taking the 1mg glimepiride, subjects may be discontinued from investigational product.

All serious adverse events will be reported.

Adverse Events will be collected from subject actually taking the IP.

Subjects will discontinue the study if one major hypoglycaemic event or recurring minor hypoglycaemic events (any recurrent events of hypoglycaemia, as judged by the investigator, not meeting the definition of major hypoglycaemic event) occur.

Randomized subjects who discontinue the study prematurely should immediately stop taking investigational product and complete the procedures described for Visit 7.

4.4 End of Treatment: VISIT 7

Physical exam contains measurement of weight, waist circumflex, pulse and blood pressure. BMI calculation will be conducted.

12 lead ECG will be conducted.

Subjects will be followed for laboratory assessment of efficacy and safety according to study plan FBG, HbA1c, CBC, AST, ALT, total bilirubin, BUN, creatinine, electrolytes, total cholesterol, triglyceride, HDL-cholesterol, urinalysis, hsCRP, adiponectin. All laboratory assessment will be done in central laboratory.

Diet and life-style counselling will be given to the subject.

DXA and abdominal CT measurement will be conducted.

Concomitant medications will be checked.

Drug accountability of investigational product and metformin will be conducted.

Subject diary will be reviewed for hypoglycaemic events.

All serious adverse events and adverse events will be reported and followed up

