### 3.9.3 Laboratory Evaluations

Results from the central laboratory will be included in the reporting for serum chemistry, hematology and urinalysis. A list of tests to be performed is included in Protocol section 5.2.1.

The following summaries will be provided for laboratory data:

- Actual value of each scheduled visit and change from baseline for each post-baseline scheduled measurement by visit (for quantitative measurements only).
- Incidence of abnormal values according to normal range criteria. Abnormalities will be classified to “Low” if smaller than the lower limit while “High” if larger than the upper limit.
- Shift from baseline according to abnormality status (Low, Normal and High) for each post-baseline scheduled measurement. For urinalysis, shift between normal and abnormal will be prepared.
- Listing of observed results for all laboratory values will be provided with abnormality status flagged.

- Additionally, Change from screening (visit 1) to each post-treatment time point will be reported for CBC, electrolytes, lipid parameters.

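### Section 4.3 and Table 1 disagree on creatinine and liver tests at Week 36; under the 4.3 list the renal discontinuation criterion has no routine scheduled trigger between Week 24 and the end of treatment

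*Protocol*

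**What the plan says.** Protocol section 4.3 lists the laboratory tests visit by visit:

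- Week 12: "Visit 4: FBG, HbA1c, AST, ALT, total bilirubin, BUN, creatinine, urinalysis"
- Week 24: "Visit 5: FBG, HbA1c, CBC, AST, ALT, total bilirubin, BUN, creatinine, electrolytes, urinalysis"
- Week 36: "Visit 6 : FBG, HbA1c, urinalysis"

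Creatinine and liver tests return at Visit 7 (section 4.4).

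Table 1 differs. Its rows "BUN/creatinine" and "AST/ALT/total bilirubin" are marked at Visits 1, 4, 5, 6, 7 and the rescue visit, so Week 36 is included. Section 4 opens by making that table the plan: "Study is planned to be conducted according to plan described in" Table 1. Section 4.3 also presents its own list as following the study plan. Section 5.2.1 names the analytes but assigns no visits, so it does not settle the matter.

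Among the situations in which product may be discontinued, section 3.9 includes "Calculated Creatinine-Clearance <60 ml/min or an increase in serum creatinine" of a stated size above baseline, confirmed by a repeat within one week. SAP 3.9.3 will summarise laboratory values and "change from baseline for each post-baseline scheduled measurement by visit". SAP 1.2 refers to Table 1 of the protocol for the schedule.

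**The concern.** The Visit 6 line in 4.3 cannot be read as shorthand. The lines for Visits 4 and 5 spell out creatinine, BUN, AST, ALT and bilirubin, and the Visit 6 line leaves them out. Someone working from 4.3 would reasonably conclude that these tests are not due at Week 36, and someone working from Table 1 would conclude that they are.

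The difference matters most for renal function, because a discontinuation criterion depends on it. Under 4.3, the last routine creatinine value that could lead to stopping product is at Week 24. The next comes at Visit 7, when treatment is ending anyway. Section 6.3.6 adds to this: deterioration in a protocol-mandated laboratory value is reported as an adverse event only if it meets a seriousness criterion or is the reason for discontinuation, although associated signs or symptoms are reported in their own right. A change without symptoms is therefore seen mainly through the scheduled tests.

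There is a smaller analytical consequence. SAP 2.2 lists patients who meet withdrawal criteria but are not withdrawn among those who may be excluded from the per-protocol set. Whether a renal criterion is detected at all can depend on which schedule was used.

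**Working it through.** The plan states no figure to reproduce. The check compares the two schedules and measures the intervals between visits.

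**Inputs.** Table 1 places Visits 3 to 7 at Weeks 4, 12, 24, 36 and 52, each with a window of ±7 days. The Table 1 rows were split into cells and aligned with its row of visit numbers. The other tests come from 4.3 and 4.4, and the outcome weeks from 2.3.

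**Post-baseline weeks by source**

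| Test | Table 1 | Sections 4.3 and 4.4 | Section 2.3 |
|---|---|---|---|
| BUN/creatinine | 12, 24, 36, 52 | 12, 24, 52 | not listed |
| AST/ALT/bilirubin | 12, 24, 36, 52 | 12, 24, 52 | not listed |
| CBC | 4, 12, 24, 36, 52 | 24, 52 | 4, 12, 24, 36, 52 |
| Electrolytes | 12, 24, 36, 52 | 24, 52 | 4, 12, 24, 36, 52 |

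The creatinine mismatch is one of several between 4.3 and Table 1. For electrolytes, none of the three sources agree.

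**Intervals between scheduled creatinine values after Week 24.** Interval = later week − earlier week. With ±1 week at each end, the range is the interval ±2 weeks.

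- Section 4.3: 52 − 24 = 28 weeks (26 to 30). Share of treatment: 28/52 = 54%.
- Table 1: 36 − 24 = 12 weeks (10 to 14), then 52 − 36 = 16 weeks (14 to 18). Longest share: 16/52 = 31%.

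The interval from Week 12 to Week 24 is 12 weeks under both, so the schedules part only after Week 24.

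**Reliability of the Table 1 marks.** The available text of the table was read by a program. Its column header is displaced, and the rows stop after the electrolytes. Two checks on the alignment point in different directions:

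- The ECG row falls on Visits 1 and 7, which agrees with 4.1 and 4.4. This supports the alignment of the columns.
- The HbA1c row is marked at Visit 3, but section 5.1.7.1 gives Visits 1, 4, 5, 6, 7 and rescue. At least one mark in the same block is therefore either an error in the source or a reading artefact.

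The creatinine and liver rows keep their blanks at Visits 2 and 3 and have the same number of cells as the visit row. The Week 36 marks are credible but should be confirmed in the source table.

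**The case against.** The strongest reply is that the protocol already ranks its sources. Section 4 says the study follows Table 1, and 4.3 defers to the study plan. If the Table 1 marks are right, Week 36 creatinine is scheduled, and the gap arises only for a site that works from the 4.3 list alone. This stands, and it makes the consequence conditional. It does not remove the contradiction, because 4.3 offers its list as that plan and no text says which prevails if they differ.

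Three stronger readings are tempting, and the documents do not support them.

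- *The renal rule cannot operate after Week 24.* Section 3.9 is permissive and not tied to scheduled visits, and its confirming repeat within a week may itself fall outside the schedule. SAP 3.1.3 provides for unscheduled measurements, and the rescue visit in 4.5 includes creatinine, though only for subjects who need rescue. The criterion loses its routine trigger and nothing more.
- *A liver stopping rule is also affected.* Section 3.9 has no specific liver threshold. Liver findings enter only through its general provision for adverse events, which covers laboratory abnormalities.
- *Sites will split, so the Week 36 chemistry summaries will rest on an arbitrary subset.* Nothing shows this. All samples go to a central laboratory, and the Laboratory Manual mentioned in section 9.2, which is not available here, may fix one panel per visit for every site. The affected SAP summaries are descriptive in any case.

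It is also fair to say that 54% is the length of an interval, not a risk. The documents give no event rate from which to estimate how many subjects would be affected.

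**Conclusion.** The point holds as an internal contradiction with a bounded safety consequence. For a site working from 4.3, the longest interval without a routine creatinine value is 28 weeks (26 to 30 with the visit windows), against 16 weeks (14 to 18) under Table 1. In that interval the 3.9 renal criterion is weakened because it depends on unscheduled tests or a rescue visit. The liver tests are a monitoring inconsistency without a stopping threshold attached.

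The conclusion rests on two assumptions: that the Week 36 marks in Table 1 are as they appear in the available text, and that some user of the protocol works from 4.3. The first can be settled by looking at the source table. The point is worth correcting because it touches a discontinuation criterion and is cheap to resolve. Confidence is medium until the source table is checked.

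**What to change.** 1. Confirm the Visit 6 marks for creatinine, BUN and liver tests in the source Table 1, and the HbA1c mark at Visit 3 against 5.1.7.1.
2. Reconcile the visit lists in 4.3 with Table 1 so that one laboratory schedule applies. Settle the CBC and electrolyte mismatches with section 2.3 in the same change, and state which text governs if any difference remains.
3. Have the clinical team confirm that the reconciled schedule supports the 3.9 renal criterion over the whole treatment period. Which text stands is their decision; no schedule is proposed here.
4. Align the by-visit laboratory and shift tables under SAP 3.9.3 with the result.

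The cost is a protocol clarification, a memo to sites and a check of the table shells. Both schedules already need blood at Visit 6 for glucose and HbA1c, so neither outcome should add a visit or a separate venepuncture. Whether any central laboratory analysis is added depends on the schedule chosen.
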